10.5. Safety Analyses

All safety analyses will be performed using the safety population.

Safety analyses will be summarized by treatment. Safety will be evaluated by the incidence of serious adverse events, incidence and severity of adverse events, incidence of permanent treatment discontinuation due to adverse events, and incidence of new clinically significant changes in clinical laboratory values and vital signs.

The treatment-emergent period is defined as the duration of time from the date and time of the first dose of any randomized study drug treatment (enzalutamide plus leuprolide, enzalutamide monotherapy, or placebo plus leuprolide) through 30 days after the last dose of randomized study drug treatment (permanent treatment discontinuation). The treatment-emergent period will include the period from first dose through potential protocol-specified suspension and potential resumption of study drug treatment before permanent treatment discontinuation. Safety data collected following 30 days after study drug suspension and during the time off study drug treatment will be analyzed and described.

Adverse events will be coded according to the Medical Dictionary for Regulatory Activities (MedDRA) and tabulated by system organ class and by preferred term within each system organ class. Tabular summaries will include the incidence overall (number and percentage of patients with treatment-emergent adverse events classified by system organ class and preferred term); incidence by intensity (severity graded according to the CTCAE, version 4), causality, seriousness, and outcome (eg, leading to discontinuation of study drug); and other presentations as appropriate.

Serious adverse events occurring before study treatment will be tabulated separately if considered related to study procedure.

Patients with the same adverse event reported more than once will be counted once at the maximum severity or strongest relationship to study drug.

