3.4. Baseline Variables

3.4.1. Study Drug, Study Treatment, and Baseline Definitions

The date of first dose (start date) of study treatment in the combination arms is the earliest date of non-zero dosing for each of the study drugs (enzalutamide/placebo or leuprolide).

The date of first dose (start date) of study treatment in the enzalutamide monotherapy arm is the earliest date of non-zero dosing of enzalutamide.

The date of last dose of study treatment in the combination arms is the latest date of non-zero dosing for each of the study drugs.

The date of last dose of study treatment in the enzalutamide monotherapy arm is the latest date of non-zero dosing of enzalutamide.

Definition of Baseline:

No windowing will be applied when defining baseline. For example, the protocol requires safety assessments to be performed within 28 days prior to randomization; however, values outside this window will not be excluded when determining baseline assessments. Any deviations from the protocol specified window will be documented as protocol deviations.

Definition of baseline for efficacy and baseline analyses

The last measurement prior to randomization will serve as the baseline measurement for efficacy and baseline analyses.

Definition of baseline for PRO

Per protocol, the first PRO assessment is planned to occur prior to dosing on Day 1; therefore, the last measurement on or prior to the day of first dose of study treatment (on or prior to randomization for patients randomized but not dosed) will be used as the baseline measurement.

Definition of baseline for safety analyses

The last available assessment on or prior to the date of first dose of study treatment (or prior to randomization for patients randomized but not dosed) is defined as the 'baseline' value or 'baseline' assessment for safety analyses. If an assessment is planned to be performed prior to the first dose of study treatment in the protocol and the assessment is performed on the same day as the first dose of study treatment, it will be assumed that it was performed prior to study treatment administration, if assessment time is not collected or is missing. If assessment times are collected, the observed time point will be used to determine pre-dose on study Day 1 for baseline calculation (this only applies for safety). Unscheduled assessments will be used in the determination of baseline.

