3.5. Safety Endpoints

Safety will be assessed through adverse event (AE) reporting, laboratory and vital sign assessments. AEs will be graded by the investigator according to the Common Terminology Criteria for Adverse Events (CTCAE) version 4.03 and coded using the Medical Dictionary for Regulatory Activities (MedDRA) version in use at the time of database release.

Safety endpoints will be summarized based on the on-treatment period, modified treatment period, or re-initiation treatment period as specified.

On-Treatment Period

The on-treatment period is defined as the time from the date of first dose of study treatment through a minimum of 30 days after last dose of study treatment, or the start day of new antineoplastic drug therapy -1 day, where the last dose of study treatment is the final dose after any suspension period due to undetectable PSA. Adverse events occurring on the same day as the first dose of study treatment will be considered to have occurred during the on-treatment period. All other assessments which occur on the same day as the first dose of study treatment will be considered baseline assessments (see Section 3.5).

Safety data collected outside the on-treatment period as described above will be listed but not summarized.

Modified Treatment Period

For patients whose treatment is suspended due to undetectable PSA at week 36 the modified period is defined as the period of time of study drug exposure starting from the date of the first dose of study drug through 30 days after last dose prior to the treatment suspension PLUS the time period starting from date of first dose at study drug reinitiation through a minimum of 30 days after last dose of study treatment, or the start day of new antineoplastic drug therapy -1 day. If date of first dose at study drug reinitiation is earlier than 30 days after last dose prior to the treatment suspension, then the modified treatment period is the same as that on-treatment period.

For all other patients the modified treatment period is the same as the on-treatment period.

Reinitiation Treatment Period

The reinitiation treatment period is defined only for patients who suspend treatment due to undetectable PSA at week 36 and subsequently reinitiate treatment and is defined as the time

period starting from date of first dose at study drug reinitiation through minimum 30 days after last dose of study treatment, or start day of new antineoplastic drug therapy -1 day.

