Treatment-Emergent Adverse Events

Treatment-emergent adverse events (TEAEs) are those events with onset dates occurring during the on-treatment period for the first time

Modified Treatment-Emergent Adverse Events

Modified treatment-emergent adverse events (mTEAEs) are adverse events occurred during the modified treatment period (ie, events occurring or worsening during the treatment suspension period after 30 days of last dose prior to treatment suspension (and prior to treatment suspension if applicable) are excluded).

Reinitiation Treatment-Emergent Adverse Events

Reinitiation treatment-emergent adverse events (rTEAEs) are adverse events occurred for the first time during the dosing period after suspension and reinitiation of study treatment as defined by the reinitiation treatment period.

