5.2.5. Definitions and Computations

Study Day

The study day for assessments occurring on or after the first dose of study treatment (eg, adverse event onset, tumor measurement) will be calculated as:

Study day = Date of the assessment/event - start date of study treatment/randomization date + 1.

The study day for assessments occurring prior to the first dose of study treatment (eg, baseline characteristics, medical history) will be negative and calculated as:

Study day = Date of the assessment/event – start date of study treatment.

The study day will be displayed in all relevant data listings.

Treatment Duration

The following durations will be calculated (of note, the data cutoff date is considered in calculation when last dose date and antineoplastic therapy date are not available):

Treatment Duration = Date of last dose of study drug – Date of first dose of study drug + 1

Treatment Suspension Duration (only for patients who suspend due to undetectable PSA at week 36) = Last Date of suspension without drug (ie, First dose after suspension-1 or Date of data cutoff, whichever occurs first) -First date of suspension +1. Treatment Suspension Duration will be missing for patients who do no suspend treatment due to undetectable PSA at week 36.

Modified Treatment Duration = Treatment duration – Treatment Suspension Duration + 1 for patients who suspend due to undetectable PSA at week 36. The Modified Treatment Duration will equal the Treatment duration for patients who do not suspend treatment due to undetectable PSA at week 36.

Treatment Duration After Reinitiation (only for patients who suspend due to undetectable PSA at week 36 and subsequently reinitiate treatment) = Date of last dose of study drug – First dose after suspension + 1. Treatment Duration after Reinitiation will be missing for patients who do no suspend treatment due to undetectable PSA at week 36 as well as patients who suspend but do not reinitiate treatment.

Long-Term Follow-up Period

Long-term follow up begins after safety follow-up. Visits repeat every 12 weeks (\pm 7 days) based on the 12-week visit schedule determined at randomization.

PSA Doubling Time Calculation

Patients' PSA doubling time will be calculated by the sponsor prior to randomization. All PSA values used for calculation will be examined during randomization stage and captured on the CRF page. To calculate PSA doubling time:

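### For men who discontinue during suspension without restarting, the SAP only lists later safety data and computes a negative treatment duration

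*SAP*

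**What the plan says.** **Safety window.** SAP 3.5 runs the on-treatment period from first dose to a minimum of 30 days after last dose, or to the day before new antineoplastic therapy, "where the last dose of study treatment is the final dose after any suspension period due to undetectable PSA". SAP 3.4.1 adds: "The date of last dose of study treatment in the combination arms is the latest date of non-zero dosing for each of the study drugs". A matching rule covers the monotherapy arm. TEAEs are "those events with onset dates occurring during the on-treatment period for the first time". For everything else: "Safety data collected outside the on-treatment period as described above will be listed but not summarized".

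**Other adverse-event sets.** Modified TEAEs leave out "events occurring or worsening during the treatment suspension period after 30 days of last dose prior to treatment suspension", and this applies to all suspended men. Reinitiation TEAEs start only at reinitiation.

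**Protocol.** Protocol 10.5 says the treatment-emergent period "will include the period from first dose through potential protocol-specified suspension and potential resumption of study drug treatment before permanent treatment discontinuation". It adds: "Safety data collected following 30 days after study drug suspension and during the time off study drug treatment will be analyzed and described".

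**Exposure.** SAP 5.2.5 counts Treatment Duration from first to last dose. It ends suspension at "First dose after suspension-1 or Date of data cutoff, whichever occurs first". Modified Treatment Duration is the first minus the second, plus 1. SAP 6.7.4 divides cumulative dose by it to get average daily dose.

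**The concern.** A man who permanently stops during suspension took his last dose near week 37, so his window closes about 30 days later. A man who restarts, however late, has every suspension event inside his window. Two men with the same event on the same day are then handled differently because of something that happened afterwards.

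That is conditioning on a post-randomization outcome. It may also be selective in an unhelpful direction. Protocol 5.3 lists adverse events and death among the reasons for permanent discontinuation, so an event during suspension that itself prevents a restart is one the TEAE tables would miss. The affected outputs are the TEAE tables, time-adjusted rates, events of special interest and laboratory summaries.

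The group is foreseen: Protocol 5.4 gives a separate safety-visit timing for men who discontinue during suspension. The same omission of permanent discontinuation as an end date carries into the exposure formula.

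**Working it through.** The plan states no figure on this point to reproduce. The check applies its own definitions.

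**Inputs.** Week 37 target day 253 (Protocol Appendix 5); 30-day window (SAP 3.5); month of 30.4375 days (SAP 5.2.6). Assumed: last pre-suspension dose on day 253, suspension from day 254, and cutoff at day 1826 (5 years).

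**1. Same event, two men.** Take an event on day 400.
- Restarts, last dose on day 1000 (assumed): window ends 1000 + 30 = day 1030. The event is a summarized TEAE.
- Discontinues in suspension after day 400, no restart: window ends 253 + 30 = day 283. The event is listed only.

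**2. Does another output cover it?** For suspension data more than 30 days after the last pre-suspension dose:

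| SAP output | Man who restarts | Man who discontinues, no restart |
|---|---|---|
| TEAEs (3.5, 6.8.1) | Summarized | Listed only |
| Modified TEAEs (3.5) | Excluded | Excluded |
| Reinitiation TEAEs (3.5) | Not covered | Not defined |
| Laboratory data (6.8.3) | Summarized | Listed only |
| Deaths (6.8.2) | Tabulated | Tabulated |

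No row is a suspension-period summary of the kind Protocol 10.5 describes.

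**3. Exposure formula, man who discontinues in suspension.**
- Treatment Duration = 253 - 1 + 1 = 253 days.
- Suspension Duration = 1826 - 254 + 1 = 1573 days, whatever the date he discontinued.
- Modified Treatment Duration = 253 - 1573 + 1 = -1319 days.
- Average daily dose for an enzalutamide patient at 160 mg/day: 253 × 160 = 40,480 mg; 40,480 / (-1319) = -30.7 mg/day.

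For cutoff day C the result is 253 - (C - 253) + 1 = 507 - C, which is negative for any cutoff after day 507 (507/30.4375 = 16.7 months). Protocol 3.4 plans about 90 months to the final MFS analysis, so such cutoffs are the normal case.

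**4. Man still suspended at cutoff.** If his last dose is set to cutoff, Treatment Duration is 1826 and the modified duration is 1826 - 1573 + 1 = 254 days. That is sensible, apart from one extra day due to the trailing + 1.

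**5. Scale, by assumption only.** The documents give no suspension, restart or event rates. Suppose 175 to 315 of 350 men in an arm suspend, and 20% of them have an event more than 30 days into suspension: 175 × 0.20 = 35 to 315 × 0.20 = 63 men. If 10% of suspended men fall in the listed-only group, with the same event risk, 3.5 to 6.3 men's events go unsummarized. At 50% it is 17.5 to 31.5.

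**The case against.** The strongest reply is that the SAP provides for men without a final dose. SAP 5.2.5 uses the cutoff date when last-dose and antineoplastic dates are unavailable. SAP 5.3.1.1 treats a man with a completely missing last-dose date, no End of Treatment page and no death as ongoing, with cutoff as last dose. A man still suspended at cutoff can be read as not yet having had his final dose. On that reading his suspension is summarized and his duration is about 254 days.

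This stands as a possible reading, so a reader should not infer that every non-restarter is excluded or has a negative duration. It does not settle the matter: SAP 3.4.1 points to the latest non-zero dose, which is known for him, and the SAP does not say the cutoff rule extends to 3.5. Neither rule helps the man who has permanently discontinued.

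Other replies stand in part:
- Protocol 10.5 also ends its period 30 days after last dose, glossed as permanent discontinuation. In this group the two dates differ, so the conflict over the window is partial. The firm mismatch is the undelivered summary of off-drug data.
- Modified TEAEs do not depend on restart, but only because they drop these events for everyone.
- Time-adjusted rates cut numerator and denominator together. The person-time kept is still selected by later restart.
- Deaths are tabulated overall. Time to first SAE (SAP 6.8.1) is not expressly limited to TEAEs, and second malignancies are reportable as SAEs (Protocol 8.5.5), apart from uncomplicated nonmelanoma skin cancers. Serious events are therefore partly protected.
- What is lost for one man is only the time from day 283 to his discontinuation. If he stops at month 14 (14 × 30.4375 = day 426), that is 143 days, about 5 months. Setting his window against that of a man followed for years would not compare like with like.

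**Conclusion.** Wrong as written for men who suspend at week 37 and permanently discontinue without restarting. Their suspension data beyond about 30 days after the last pre-suspension dose are listed only, while the same data are summarized for men who restart. For men still suspended at cutoff the SAP is ambiguous. For all suspended men, no SAP table provides a summary dedicated to the off-drug period.

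The formula error is certain for the discontinuing group whenever cutoff falls after day 507: -1319 days at day 1826. It rests on last dose at day 253; a shift of a day or so changes nothing of substance. It affects a descriptive exposure measure, not efficacy.

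A reader might infer that the TEAE comparison is biased between arms. The documents do not show this. Restart is triggered by PSA, and undetectable PSA at week 36 and time to hormonal resumption are themselves between-arm endpoints, so equal rates cannot be assumed. But no rates are given, and neither the size nor the direction of any imbalance can be stated.

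**What to change.** 1. **On-treatment period (SAP 3.5).** For suspended men who do not restart, run it through suspension to the earliest of 30 days after permanent discontinuation, the day before new antineoplastic therapy, or data cutoff. State that men still suspended at cutoff follow the same rule.
2. **Suspension-period summary.** Add an adverse-event table by arm for all suspended men, starting 30 days after the last pre-suspension dose, with person-time denominators. Stop person-time where recording stops: non-serious events are not recorded after new anticancer therapy (Protocol 8.1.6), and the safety visit of a man who discontinues in suspension may fall any time after 28 days from last dose (Protocol 5.4).
3. **Durations (SAP 5.2.5).** End Treatment Suspension Duration at the earliest of the day before restart, permanent discontinuation or cutoff, and use the same end date for Treatment Duration when there is no restart. For discontinuation on day 800 this gives 800 - (800 - 254 + 1) + 1 = 254 days. Dropping the trailing + 1 would give the 253 days on drug.
4. **Cross-reference.** SAP 6.8 points to 5.2.5 for the on-treatment definition, which is in 3.5. Correct this at the same time.

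The cost is SAP wording, reprogramming of derived dates and one additional table. Adverse events are already reviewed at the 12-weekly visits during suspension, so no new data are needed. The change can still be made for the safety summaries planned after protocol amendment 5.

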12. Absolute neutrophil count $<1500/\mu\text{L}$, platelet count $<100,000/\mu\text{L}$, or hemoglobin $<10\text{ g/dL}$ (6.2 mmol/L) at screening. NOTE: May not have received any growth factors or blood transfusions within 7 days before the hematology values obtained at screening.
13. Total bilirubin (TBili) ≥ 1.5 -times the upper limit of normal (except patients with documented Gilbert's disease), or alanine aminotransferase (ALT) or aspartate aminotransferase (AST) ≥ 2.5 -times the upper limit of normal at screening.
14. Creatinine $>2\text{ mg/dL}$ ($177\text{ }\mu\text{mol/L}$) at screening.
15. Albumin $<3.0\text{ g/dL}$ (30 g/L) at screening.
16. History of seizure or any condition that may predispose to seizure (eg, prior cortical stroke or significant brain trauma). History of loss of consciousness (unless of cardiac origin) or transient ischemic attack within 12 months before randomization.
17. Clinically significant cardiovascular disease including the following:
 - Myocardial infarction within 6 months before screening;
 - Unstable angina within 3 months before screening;
 - New York Heart Association class III or IV congestive heart failure or a history of New York Heart Association class III or IV congestive heart failure unless a screening echocardiogram or multigated acquisition scan performed within 3 months before the randomization date demonstrates a left ventricular ejection fraction $\geq 45\%$;
 - History of clinically significant ventricular arrhythmias (eg, sustained ventricular tachycardia, ventricular fibrillation, torsades de pointes);
 - History of Mobitz II second-degree or third-degree heart block without a permanent pacemaker in place;

- Hypotension as indicated by systolic blood pressure <86 mm Hg at screening;
- Bradycardia as indicated by a heart rate of ≤ 45 beats per minute on the screening electrocardiogram (ECG);
- Uncontrolled hypertension as indicated by a minimum of 2 consecutive blood pressure measurements showing systolic blood pressure >170 mm Hg or diastolic blood pressure >105 mm Hg at screening.

18. Gastrointestinal disorder affecting absorption.
19. Hypersensitivity reaction to enzalutamide or any of the capsule components, including Labrasol, butylated hydroxyanisole, and butylated hydroxytoluene.
20. Contraindication to the use of leuprolide, such as a previous hypersensitivity reaction to an LHRH analogue or any of the excipients in the leuprolide injection.

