Subgroup and supplemental tabulations of TEAEs by categorized treatment group, Grade 3 and higher TEAEs by categorized treatment group, and serious TEAEs by categorized treatment group will be created as shown in Table 10.

Group Variable	Subgroups
Study Day Cut Points	0-30 days after initiation of study drug
	1-37 weeks days after initiation of study drug
	>37 weeks after initiation of study drug,
	Denominator for the above categories will be those patients that are on treatment at the beginning of the period.
	Adverse events will be assigned to day categories based on the treatment day of the start date (or worsening date) of the adverse event. Study days after initiation of study drug use the study day computations presented in Section 5.2.5.
Age (years)	<65
	≥65
	<75
	≥75
	<85
	≥85
Baseline Body Mass Index	BMI Underweight: BMI is less than 18.5.
	Normal weight: BMI is 18.5 to 24.9.
	Overweight: BMI is 25 to 29.9.
	Obese: BMI is 30 or more
Geographic Region	North America
	Europe
	Rest of the World
History of Cardiovascular Disease	Yes
-	No

Table 10.Subgroup and Supplemental Tabulations of Treatment-Emergent
Adverse Events (TEAEs)

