6.8.4. Events of Special Interest

The following TEAEs of special interests will be summarized for the overall safety population and by SOC and PT for each treatment group.

- Falls
- Fatigue
- Fracture
- Secondary primary malignancies
- Convulsions (seizure)
- Neutrophil count decreased Loss of consciousness
- Cognitive and memory impairment
- Hypertension
- Hepatic disorder
- Ischemic heart disease (IHD)
- Other selected cardiovascular events
- Posterior reversible encephalopathy syndrome (PRES)
- Renal disorder
- Thrombocytopenia
- Musculoskeletal Events
- Severe cutaneous adverse reaction (SCAR)
- Angioedema
- Rash

Additionally, for the following special adverse events, Kaplan-Meier methods will be used to display the time to the first occurrence of each event.

• Secondary primary malignancies

- Hypertension
- Selected cardiovascular events

The TEAEs of special interests will be defined based on a list of MedDRA Preferred Terms confirmed by Pfizer Pharmacovigillance. A final list will be provided to programming prior to database release.

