Appendix 2 provides the definition of AEs of special interests.

The treatment emergent hypertension incidence will be summarized by baseline charatristics including baseline history of dyslipidemia, diabetes mellitus, cardiovascular, hypertension, BMI and age subgroup. The associated list for dyslipidemia and hyperglycemia standardized MedDRA queries (SMQs) will be provided to programming prior to database release.

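### The SAP defines treatment-emergent events by first onset on treatment only, so read literally an adverse event that starts before the first dose and rises in grade on drug is not counted

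*SAP*

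**What the plan says.** SAP 3.5 defines three sets of events.

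- **TEAE:** these "are those events with onset dates occurring during the on-treatment period for the first time". There are two conditions, an onset date inside the period and a first occurrence. A change in grade is not mentioned.
- **Modified TEAE (mTEAE):** adverse events in the modified treatment period. A parenthesis removes "events occurring or worsening during the treatment suspension period after 30 days of last dose prior to treatment suspension".
- **Reinitiation TEAE (rTEAE):** these "are adverse events occurred for the first time during the dosing period after suspension and reinitiation of study treatment". Again worsening is not mentioned.

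SAP 6.8.1 and Protocol 10.5 add no worsening rule. Protocol 10.5 sets only the time window.

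Two later parts of the SAP use the TEAE set in ways that bear on this. Table 10 in SAP 6.8.1 tabulates TEAEs by time since first dose and assigns them "based on the treatment day of the start date (or worsening date) of the adverse event". SAP 6.8.4 opens with "The following TEAEs of special interests will be summarized for the overall safety population and by SOC and PT for each treatment group", and its list includes hypertension. It closes with a further plan: "The treatment emergent hypertension incidence will be summarized by baseline charatristics including baseline history of dyslipidemia, diabetes mellitus, cardiovascular, hypertension".

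**The concern.** The TEAE set feeds most of the planned safety output: incidence by grade and relationship, serious TEAEs, events leading to discontinuation or dose change, time to first Grade 3 or higher TEAE, the Table 10 subgroups (including history of cardiovascular disease) and every event of special interest. SAP 3.5 also says that safety data from outside the on-treatment period are listed but not summarized. An event recorded as Grade 1 in screening that reaches Grade 3 on drug would, on the literal rule, appear in none of these summaries.

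The SAP is also not consistent with itself. Two programmers could build different TEAE tables from it, one by first onset alone and one by onset or worsening, and each could cite a section in support.

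**Working it through.** No arithmetic applies. The check sets the relevant sections side by side.

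1. **Can adverse events with pre-dose onset be in the database?** Yes. Protocol 8.1.4 and note 17 of Appendix 5 start collection at informed consent. Protocol 5.1 sets screening at day -28 to day -1, and consent may be obtained earlier. SAP 5.3.1 has a rule for events whose partial start date places them before treatment.

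2. **Does any section bring such an event back in if it worsens?** No. SAP 5.3.1 classifies by start date alone. SAP 6.8.1 takes the TEAE set as given.

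3. **Trace one case.** Take a single adverse event record with onset in screening at Grade 1, rising to Grade 3 after dosing begins and before any suspension.
   - TEAE rule: the onset date is before the on-treatment period, so it is not a TEAE.
   - mTEAE rule: no first-onset condition is stated. Worsening is excluded only in the off-drug interval, which implies that worsening elsewhere may count. The event could be an mTEAE.
   - rTEAE rule: it did not first occur after reinitiation, so it is not an rTEAE.
   - Table 10: it has a worsening date that the table could use, but the table holds only TEAEs, so the event never reaches it.

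4. **Check the nesting.** The modified treatment period is the on-treatment period with the off-drug suspension interval removed (from 30 days after the last dose before suspension). Modified TEAEs should therefore be a subset of TEAEs. In the traced case an event can be the first without being the second.

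5. **Check the hypertension summary.** Protocol exclusion criterion 17 bars only "Uncontrolled hypertension as indicated by a minimum of 2 consecutive blood pressure measurements" above stated limits, so men with controlled hypertension can enrol. If a first occurrence is judged against medical history, the row for men with a history of hypertension is emptied or distorted. If it is not, the row depends on how sites record aggravation. The SAP does not say which applies.

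6. **Look for cover elsewhere.** Table 12 in SAP 6.8.5 reports blood pressure change from baseline, including thresholds combined with change. SAP 6.8.3 has shift tables from baseline grade to worst later grade for laboratory values. These catch worsening in blood pressure and laboratory data. They do not repair the adverse event tables, and they do not reach events such as fatigue, falls or ischemic heart disease.

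**The case against.** The strongest reply is that the rule concerns adverse event records, not diagnoses. Long-standing hypertension is medical history, which is collected and coded separately. If its aggravation on drug is entered as a new adverse event, that record has an on-treatment onset date and could be a TEAE. On this view the plan to tabulate hypertension by history shows that the authors expect events in such men. This stands as far as it goes. The documents do not say how aggravation is entered, or whether a first occurrence looks back to medical history. The exclusion is clear only for events that start between consent and first dose and then worsen under the same record.

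It can also be said that the two mentions of worsening prove little. One sits in a parenthesis about what is excluded, and the other is a rule for allocating events to time categories. Either could refer to an event that began on treatment and later rose in grade. That is fair: neither shows that pre-dose events are meant to count, and the rTEAE definition is first-occurrence only, like the TEAE definition. But the SAP then gives worsening a role in two places without saying what that role is in the definition on which both depend.

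Finally, the primary analysis is complete and the study is unblinded (Protocol 3.1 and 18.1), so a redefinition now could break comparability with safety results already produced. This does not remove the problem. It bears on how the fix is made.

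**Conclusion.** The point holds as a stated rule that, followed literally, leaves out pre-dose adverse events that worsen on drug, and that does not fit Table 10, the mTEAE text or the hypertension-by-history summary. It rests on reading onset and first occurrence as written, and on worsening being kept under the existing record. If sites enter worsening as a new event, some or all of these cases may already be counted.

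The size cannot be derived, because the documents give neither the frequency of pre-existing conditions nor the rate at which they worsen. A reader might infer that hypertension is badly undercounted and that the history table will show falsely low risk. The documents do not support that. Suppose, purely as an assumption, that 30% to 60% of men have a history and that new-or-worsened incidence is 20% without and 25% with one. If no event in men with a history is counted, the share captured is:

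- history 30%: 0.7 × 0.20 / (0.7 × 0.20 + 0.3 × 0.25) = 0.140 / 0.215 = 65%
- history 60%: 0.4 × 0.20 / (0.4 × 0.20 + 0.6 × 0.25) = 0.080 / 0.230 = 35%

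If every aggravation is entered as a new event and counted, the share is 100% in both cases. The answer is set by the unknown recording practice and by inputs found nowhere in the documents, so no figure should be attached to this point.

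A reader might also infer that the SAP's other definitions include worsening. Only the mTEAE text does so, and only by implication.

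**What to change.** Amend SAP 3.5 so that each definition has its own window and reference grade:

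- **TEAE:** an event that starts, or increases in CTCAE grade from its level before the first dose, during the on-treatment period.
- **mTEAE:** the same rule within the modified treatment period, still excluding onset or worsening in the off-drug suspension interval.
- **rTEAE:** an event that starts, or increases in grade from its level before reinitiation, during the reinitiation treatment period.

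One identical sentence for all three would not work. The on-treatment period runs through suspension, so reusing its wording would bring off-drug events back into the modified set.

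Then align the two dependent outputs. In Table 10, assign each event by the date on which it met the definition. In SAP 6.8.4, state what counts as treatment-emergent hypertension in a man with a history of it. Add a line on how aggravation of a medical-history condition is recorded and classified.

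The change is a few sentences, and no efficacy analysis is affected. It still matters, because SAP 6.8 plans further safety summaries after protocol amendment 5. The costs are that incidences may rise in all arms and that the definition would change after unblinding. To keep comparability with safety results already produced, retain the first-onset tabulation as a supplementary table and record the date of and reason for the change. If existing programs already count worsening, the edit only brings the SAP into line with them.
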